### C. Recruitment and Retention

**Participant recruitment.** Low-income mothers and their infants (N=300, for a final effective sample of 200) will be participants in the study. Active participants will be low-income mothers and their infants (6mo-old at enrollment) drawn from mothers who are enrolled in HVP services at the Healthy Families America site/chapter in Antelope Valley, CA. Home visitors providing the HVP services will introduce the study to mothers, and study Assessment Workers will obtain written consent. Home visitors will clarify with mothers that their refusal to participate in the study is not affecting the services they provide. In our experience from our pilot research, families feel comfortable to refuse if they do not wish to participate. Of note, 90% of families receiving *Healthy Families America* HVP services choose to enroll in enhancement studies when offered (i.e., when a module is added to the core curriculum and evaluated). These rates are consistent with our pilot work.

**Inclusion/exclusion criteria.** Participants will be ineligible if either parent and/or child have a Dx of eating disorders (e.g., Anorexia Nervosa), Schizophrenia or Obesity-related syndrome (e.g., Prader Willi). Participants enrolled in a weight-loss program will be ineligible.

**Retention.** Using conservative estimates, we anticipate that 25% of mothers enrolled will drop out of home visiting services over the 12-month study. Consequently, we will oversample at enrollment (N=300) to ensure an effective sample of 200 mothers and infants. We have learned a great deal about retaining mothers through our prior pilot studies. We attribute retention in part to our persistent efforts and abilities of the HVP home visitors, but also believe that there are unique features of home visited mothers that facilitate retention in a research study. For example, many of these mothers are socially isolated, and opportunities to exchange with their home visitor can be highly rewarding for mothers. We will use multiple strategies to retain the sample over the 12months of the implementation and assessments. We will rely on approaches widely used in studies of high-risk populations: (1) a gift card in the amount of \$25 at each data collection, with all incentives paid after each assessment/data collection *regardless of whether they complete the study*; (2) frequent contact with participants to maintain engagement because we believe that open communication between the team and participants is critical; (3) quarterly newsletters to update participants about study activities; (4) acknowledging birthdays; (5) participants are given a reminder phone call the day before the weekly visits and assessment sessions (or on Fridays for Monday assessment sessions).

**Informed consent procedure.** Informed consent, approved by the appropriate IRB, will be obtained by Antelope Valley Partners for Health assessment workers who are trained by our research team. All mothers that are enrolled in HFA's HVP services by Antelope Valley Partners for Health and Children's Bureau will receive a detailed explanation of the protocol, including any potential benefits and risks (in English or Spanish). Mothers will be required to sign the consent form (in Spanish or English) and provide consent for their infants. Only participants from whom consent is obtained will be involved in the study. Signed consents will be kept in the participants' files in locked filing cabinets. Each participant will receive a copy.

**Waiver.** No waiver or modification of consent is being requested from the IRB.

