
**C.3. Participants.** Participants will be low-income mothers/infants (6mo at enrollment) *who are already receiving services from our HVP partner (Figure 6)*. Thus, study enrollment does not require that we recruit more families than our HVP partner is already enrolling. Mothers are enrolled in HVP services through outreach and screening pre-partum, in English or Spanish, at community health centers and hospitals. In order to be eligible mothers must meet a number of (but not all) risk criteria (e.g., low-income, housing instability). Enrolled mothers are matched to a home visitor (nurse) based on culture and language. **Recruitment.** Assessment workers (distinct from home visitors delivering services) who enroll families into services will introduce the study to mothers and obtain written consent. They will clarify with mothers that their refusal to participate in the study will not affect their receipt of any other services provided by the HVP. In our experience, families feel comfortable refusing if they are not willing to participate. Mothers/infants will be ineligible if they have any of the following conditions: eating disorders (e.g., bulimia nervosa), schizophrenia, and obesity-related syndrome (e.g., Prader Willi). Participants enrolled in a weight-loss program will be ineligible. Based on our pilot work, we expect to recruit 70% Hispanic/Latino, 13% African American, 8% White, 5% American Indian/Alaskan, 4% mixed race. **Retention.** We have learned a great deal about retention through our pilot work. For instance, most attrition from HVP services occurs in the first six months of services. Therefore, to maximize retention, mothers will be invited to participate in the study *after six months of home visits*. The unique relationship between home visitors and mothers facilitates subsequent retention, as many of these mothers are socially isolated and home visitors are important confidants and supports. We will use multiple strategies that are effective for high-risk populations to further retain the study sample: (1) gift cards of \$25 at each data collection, with all incentives paid after each assessment; (2) frequent contacts to maintain engagement and foster open communication; (3) quarterly newsletters to update subjects about study activities; (4) acknowledging birthdays and milestones; (5) reminder phone calls the day before the weekly visits and assessment sessions. **Randomization.** Randomization will be at the level of home visitors, who deliver the HVP (cluster randomization). Home visitors who serve mothers that are participating in the proposed study will be randomly assigned to deliver either HVP only or HVP+COPE. Potential concerns with randomizing by home visitors are feasibly addressed in this study. First, the likelihood of

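### The Human Subjects section has home visitors, who are the randomised units, introduce the study and explain refusal; section C.3 gives both tasks to separate assessment workers

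*Combined protocol and SAP*

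**What the plan says.** Protection of Human Subjects, section C (Recruitment and Retention), under Participant recruitment, states: "Home visitors providing the HVP services will introduce the study to mothers, and study Assessment Workers will obtain written consent". The next sentence reads: "Home visitors will clarify with mothers that their refusal to participate in the study is not affecting the services they provide".

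Section C.3 (Participants), under Recruitment, states: "Assessment workers (distinct from home visitors delivering services) who enroll families into services will introduce the study to mothers and obtain written consent". It continues: "They will clarify with mothers that their refusal to participate in the study will not affect their receipt of any other services" that the programme provides. Section C.5 (Measurements) agrees with C.3, since it describes assessment workers as trained in screening and recruiting for this project. Section C.1 (Design overview) describes them as blinded to allocation.

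The home visitor is the unit of randomisation. C.3, under Randomization, says: "Home visitors who serve mothers that are participating in the proposed study will be randomly assigned to deliver either HVP only or HVP+COPE". Visitors in the COPE arm receive their own training (C.2, Treatment fidelity), and training and supervision are kept apart by arm (C.3).

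Two further statements bear on the risk. The Human Subjects recruitment paragraph expects that 90% of families in these services "choose to enroll in enhancement studies when offered". The informed consent paragraph says that all mothers enrolled in the home visiting services "will receive a detailed explanation of the protocol, including any potential benefits and risks".

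**The concern.** In a cluster-randomised trial, allocating the clusters at random balances the visitors. It does not protect the make-up of the families if they are recruited after allocation by someone who knows the arm. That person can, without intending it, present the study more or less warmly, or to some families more than others. The arms may then enrol different kinds of families.

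C.3 guards against this by giving the introduction to staff who do not deliver services and who, according to C.1, do not know the arm. The Human Subjects wording removes that safeguard for the introduction and the refusal explanation.

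The quality of consent is also involved. C.3, under Retention, notes that many of these mothers are isolated and that "home visitors are important confidants and supports". Under the Human Subjects wording, the person telling a mother that she may safely refuse is the person who provides her services.

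**Working it through.** The plan gives no figure that depends on this point, so the check is mainly a comparison of text.

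**1. Who does what**

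| Task | Human Subjects, section C | C.3 | Elsewhere |
|---|---|---|---|
| Introduce the study | Home visitor | Assessment worker | C.5: assessment workers trained to screen and recruit |
| Explain that refusal is harmless | Home visitor | Assessment worker | Not stated |
| Take written consent | Assessment worker | Assessment worker | Informed consent paragraph: assessment worker |

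The conflict covers the first two rows only. Both texts are current; neither is a change log.

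**2. Who knows the arm**

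Assessment workers are blinded (C.1). Home visitors cannot be once allocated, because they deliver the arm and are trained and supervised by arm (C.2, C.3).

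**3. Whether allocation comes before the approach**

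The plan does not say.
- The Power Analysis in C.6 has 30 visitors recruited and randomised and then describes inviting families, which reads as one step at the start.
- The C.3 Randomization sentence refers to visitors who serve mothers already taking part, which can be read as enrolment first.
- C.1 has families enrolled on a rolling basis over 24 months, study months 6 to 30.
- 300 families over 30 visitors is 300 / 30 = 10 families per visitor on average. Unless all of a visitor's families consent before she is allocated, which no section requires, her later families would be approached after allocation. This is an inference from the rolling design, not a statement in the plan.

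**4. Which route is open**

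Under C.3, mothers are matched to a visitor on entering services and invited to the study after six months of visits. The visitor's arm therefore does not determine which mothers she is matched to if allocation follows matching. What remains open is which of her families are approached and persuaded.

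**5. Scale of refusals at the plan's uptake**

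- If 300 is the number enrolled (Human Subjects, section A): 300 / 0.90 = 333 approached and 333 − 300 = 33 refusals, or about 17 per arm if the arms are equal (assumption).
- If 300 is the number invited (Power Analysis): 300 × 0.10 = 30 refusals, or 15 per arm on the same assumption.

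These are counts, not a bias. They do not include families who are never approached. Turning them into a bias would need uptake by arm and the difference between refusers and joiners on the outcome. The documents give neither.

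**The case against.** The strongest reply is that this is a drafting inconsistency and not a chosen design. C.3 and C.5 agree that assessment workers recruit, and every section leaves written consent with them; only the Human Subjects paragraph departs. That stands, and it is why the remedy is a correction of wording. It does not remove the conflict, because nothing says which text governs.

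Second, the consent paragraph promises an explanation to every mother enrolled in services. Taken literally, this largely rules out selective approach. It is a real limit on the risk. However, the sentence does not say who gives the explanation or whether it comes before or after the visitor's introduction, and it does not address persuasion.

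Third, 90% uptake leaves few refusals. That also stands, but the figure is not given by arm and concerns families to whom the study has been offered.

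A reader might infer that the arms will enrol different families. The documents do not support that: the bias needs the Human Subjects wording to prevail and the visitor to know her arm before the approach, and neither is settled. The training row in the Table 7 timeline does not settle it either, because it says nothing about allocation.

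A reader might also want to express the bias as a share of the pilot effect of 0.4 in the Power Analysis. That has no basis. The pilot figure is for children's weight velocity, whereas nothing in the plan says how refusers would differ on that scale. The planned analyses also use change and baseline adjustment, so a shift in who enrols need not carry over one for one.

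**Conclusion.** The contradiction is certain: two current sections assign the introduction and the refusal explanation to different staff, one group blinded and the other the randomised units. The consequence is conditional. If the Human Subjects wording is followed after visitors are allocated, someone who knows the arm could influence which families join. The covariates in C.6 and the baseline outcome in the Aim 1 models would correct only the measured part of any resulting difference.

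The universal explanation and the high expected uptake make a large effect less likely but do not exclude one. The size cannot be derived from the documents. The point should be corrected because it concerns a basic safeguard of a cluster-randomised trial and costs very little to settle. It is not evidence that recruitment was or will be biased.

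**What to change.** 1. In Protection of Human Subjects, section C, replace the two home-visitor sentences with the rule already in C.3 and C.5: blinded assessment workers introduce the study, explain that refusal has no effect on services, and take consent.
2. In C.3, under Randomization, state whether visitors are randomised before or after their families consent, and make the Power Analysis wording agree.
3. Report the numbers of families approached and consented by arm. Assessment workers can log these by visitor, with the arm added later by someone else, so that they stay blinded.

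Items 1 and 2 are wording changes and need no new staff role, since assessment workers are already trained to recruit and already take consent. Item 3 needs a short log. Without it, differential recruitment could not be examined afterwards.

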### D. Protection Against Risk

**Safety reviews.** The PIs will review the safety and progress of this study on a monthly basis. The PIs and the IRBs will review this protocol on a continuing basis for subject safety and include results of the review in the annual progress reports submitted to NIH. The annual reports will include a list of adverse events and address: 1) whether adverse event rates are consistent with pre-study assumptions; 2) reasons for dropouts from the

study; 3) whether all participants met entry criteria; and 4) whether continuation of the study is justified on the basis that additional data are needed to accomplish the stated aims of the study.

It is also important to note that Healthy Families America home visitors are expertly trained and experienced in handling situations they encounter while working with at-risk families. All home visitors receive extensive training in cultural competency, substance abuse, reporting child abuse, domestic violence, drug-exposed infants and children, and linkage to services in their community. Home visiting staff further receive intensive training specific to their role (i.e., assessment, home visitation, identifying at-risk families, completing standardized assessments, phlebotomy, mental health referrals, promoting preventive health care, securing medical homes, immunizations, utilizing creative outreach efforts, establishing and maintaining trust with families, building upon family strengths, developing individual family support plans, determining the safety of the home, teaching parent-child interaction, managing crisis situations, etc.). Staff further receive weekly supervision, ongoing developmental training, and have limited caseloads (10-15 families) to meet families' needs.

**Monitoring plan.** The study's data safety and monitoring plan will entail several components, overseen Principal Investigators (Drs. [name] and [name]):

1. All University of Southern California (USC) and University of Alabama at Birmingham IRB policies and continuous reporting requirements will be followed in conducting the proposed study. Any actions taken by the IRB as part of its continuing review will be immediately reported to NIH.
2. The PIs will implement and monitor procedures to ensure that each mother provides informed consent and that all data remains confidential. This will also include a rigorous data management protocol to optimize data entry, accuracy/checking, and retrieval. Data will be stored in password-protected files accessible only to the investigators and staff under their supervision. In the database, only an ID code number will identify subjects. A list linking names and other identifiers with their ID codes will be stored in a separate file with a separate password. All original paper surveys and case report forms will be stored in locked file cabinets. The PIs will review all data collection forms for completeness and accuracy of the data and for protocol compliance. In the case of a breach of confidentiality or other adverse event, the Principal Investigators will report the event to the IRB and the appropriate NIH officials, and appropriate procedural changes will be implemented to prevent future breaches or adverse events.
3. An internal committee comprised of the projects' Principal Investigators (Dr. [name] will serve as the chair of the committee and [name] will act as clinical training and supervisor chair) and the On-Site Project Director ([name] at Antelope Valley Partners for Health) will meet quarterly to assess: participant recruitment, accrual, and retention; data quality and timeliness; participant risk versus benefit; and the development of external conditions that could potentially affect the study. Significant problems or adverse events will be reported immediately to the USC and UAB IRBs, NIH, or FDA (if relevant).
4. As part of their training for the study, all personnel who will interact with subjects will receive instruction in the completion of an adverse event reporting form. In response to any adverse event, these forms will be completed promptly and returned to the corresponding study team supervisor, who in turn will report the information to the Principal Investigators.
5. An external Data Safety Monitoring Board (DSMB), not connected to USC, UAB or the research project, will convene twice annually, via teleconference, to review the progress of the study, ensure adequate recruitment of minority subjects, and to monitor safety concerns. Key members of the research team will co-participate in the conference calls. The DSMB will consist of five to-be-named individuals from outside USC: (1) a home visitation program consumer (parent, most likely a mother) (2) a child services advocate; (3) a layperson; (4) a home visitation program stakeholder; (5) a health disparities researcher and (6) a mental health professional. The DSMB will meet by phone conference two times within each of the project's 5 years. Their function will be to review the progress of the study, ensure adequate recruitment of minorities into the sample, and monitor the study with respect to the safety and well-being of the research patients.
6. Safety officer. [name], DO is a pediatrician at the Antelope Valley Community Clinic. [name] will serve as safety officer on this project to ensure the protection, safety and satisfaction of mothers and staff throughout the many facets of the project. [name] will serve as contact-person to family participants, service providers, and all project staff to report problems or areas of concern regarding project implementation for resolution with investigators.

**Additional protections for pregnant women, human fetuses, and neonates involved in research.** This study involves parents and their infants (6mo at enrollment). This research does not involve women who are pregnant. If a mother becomes pregnant during the study, she will continue to receive HVP services, but she will not be involved in the study.

**Potential benefits of the proposed research to human subjects and others.** The potential benefits of this study include better management of postpartum weight-loss among mothers involved in home visitation programs and healthier growth trajectories for their infants. This study will also help researchers and professionals understand how home visitation programs can be used as a vehicle for early childhood obesity prevention. Participants will benefit by receiving a nutrition and physical activity module at no cost. Thus, the benefits of this project to the individual and society greatly outweigh the risks.

**Importance of the knowledge to be gained.** HVPs serve at-risk families, including low socioeconomic status (SES) and minority families, who are also at the highest risk of obesity. HVPs currently address multiple areas of mother and child health and development, but they have yet to be tested as a viable and effective infrastructure for obesity prevention in early childhood. The proposed study seizes an untapped opportunity to test this potentially cost-effective, scalable and sustainable model of obesity prevention. This represents a unique opportunity to test an innovative model of care for childhood obesity. Findings will inform health policies at local, state, and federal levels, as home visitation programs are already implemented in many U.S. urban and rural areas and serve a large proportion of low-SES and minority families. Building a healthy lifestyle intervention into this infrastructure makes it possible to reach families who are most at risk for poor nutrition, a first step toward decreasing disparities. This research is particularly timely with stable funding for HVPs from the Affordable Care Act.

**Risk-to-benefit ratio.** The risks to the participants are minimal and procedures are in place to reduce the risk and minimize the impact of adverse events. The potential gains of this project, including the adoption of healthier behaviors for mothers and their infants, healthier growth trajectories for children at high-risk for overweight/obesity, and the evaluation of a model for obesity prevention through existing home visitation programs, outweigh the risks.

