complete rigorous training to learn the HVP curriculum and meet the requirements of Healthy Families America (the HVP model we are partnering with). They receive weekly supervision to review progress and address issues. (3) Home visitors delivering COPE receive a 2-day initial training and annual refresher courses from [name] and the onsite Health Families America dietitian and nutritionist, with scripted manuals and materials. [name] further reviews 25% of the sessions to monitor fidelity. (4) Weekly supervisions (home visitors) and bi-annual focus groups (families, home visitors, and Community Advisory Board) are conducted to review progress, dosage and timing of delivery, and provide the opportunity to resolve problems or issues encountered. (5) Intervention components are delivered in the home or at specified community-run settings (e.g., community garden), and meetings and supervisions with home visitors implementing different arms are held on separate days (at Antelope Valley Partners for Health) to minimize the risks of contamination. COPE supervision is embedded in the weekly supervision home visitors already receive to monitor their services. **Potential burden or weakening of HVP curriculum.** Potential concerns related to adding material to the existing HVP curriculum include (1) diluting or weakening HVPs' outcomes in other areas (e.g., parenting skills, maternal depression), and (2) increasing the burden on HVP staff and families. Our formative evaluation and pilot work indicate that these concerns are unfounded. COPE was designed collaboratively with our HVP partners (who are experienced in integrating new enhancement modules into the HVP curriculum) so that it would complement other program goals. For instance, home visitors report that COPE cooking and tasting activities are used to strengthen mother-child bonding and parenting skills (a standard HVP benchmark area). HVP directors also found no differences between HVP+COPE and HVP only families on HVPs' benchmark areas set by the Health Resources and Services Administration (i.e., maternal and newborn health; child abuse and neglect and emergency department visits; crime or domestic violence; family economic security; and coordination and referrals for other community resources and support). Concerns that COPE may overly burden families and lead to greater attrition was also not supported, as the dropout rate was considerably *lower* among mothers in the HVP+COPE group than among mothers in the HVP only group in our pilot study. These findings suggest that the addition of COPE does not weaken other HVPs' targeted outcomes, or overly burden families and home visitors. We will continue to monitor these outcomes throughout the implementation.

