### B. Potential Risks/Adverse Events and Procedures Used to Minimize the Risks

For purposes of monitoring and reporting adverse events, the following definitions will be used:

**Adverse event (AE):** any untoward medical occurrence that may present itself during treatment or administration of an intervention, and which may or may not have a causal relationship with the treatment. Adverse events could arise from the study (e.g., breach of confidentiality) or could arise because of the population under study (e.g., a mother reports extensive use of drugs).

**Serious adverse event (SAE):** Any medical occurrence that results in death; is life-threatening; requires inpatient hospitalization or prolongation of existing hospitalizations; creates persistent or significant disability/incapacity, or a congenital anomaly/birth defect. Such an event could include suicidal ideation or attempted drug overdose or withdrawal, etc.

**Adverse events monitoring.** Each participant (mother and infant) will be evaluated for any adverse events. All events will be graded by their attribution (unrelated to protocol; or possibly, probably, or definitely related to protocol). Any event reported to the Principal Investigators or to designated research associates by the subjects or Antelope Valley Partners for Health nursing and medical staff, which also meets the event criteria, will be carefully documented in a report submitted to the IRBs. The report will include a description of the event; when and how it was reported; any official charts, records, or documentation to corroborate the event or the reporting of the event; and an action plan to prevent future occurrences. All adverse events will be graded as mild, moderate, or severe. Any severe and/or unanticipated adverse event will be immediately reported to the IRBs (within 48 hours of occurrence or recognition) and NIH. All adverse events will be summarized annually and submitted to the IRBs and NIH. Any action resulting in a temporary or permanent suspension of this study (e.g., IRB actions) will be reported to the NIH.

**Physical risks.** There are minimal physical risks added from participating in this study. All lifestyle dietary and physical activities suggested are in line with national guidelines. Recommended physical activities are low impact and unlikely to create discomfort for participants.

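### Adverse-event rates are to be judged against pre-study assumptions that the plan never states, and no safety review is set up to show events by randomised arm

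*Combined protocol and SAP*

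**What the plan says.** Human Subjects section D (Safety reviews) lists four items for the annual progress report. Item 1 is "whether adverse event rates are consistent with pre-study assumptions". The report also contains a list of adverse events.

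Section B of the same part describes the expected risk in words only: "There are minimal physical risks added from participating in this study". Events are classified by severity and by attribution ("All events will be graded by their attribution (unrelated to protocol; or possibly, probably, or definitely related to protocol"), and "All adverse events will be summarized annually and submitted to the IRBs and NIH".

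Under the Monitoring plan in section D (item 5), an external DSMB convenes twice a year "to review the progress of the study, ensure adequate recruitment of minority subjects, and to monitor safety concerns". The same item says: "Key members of the research team will co-participate in the conference calls". It describes no closed part of the call and no report format.

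The Analytic Plan (C.6) contains no safety analysis. The nearest thing to a comparison between arms is in C.2, on the pilot: "HVP directors also found no differences between HVP+COPE and HVP only families on HVPs' benchmark areas". Those areas include child abuse and neglect and emergency department visits, and the section adds: "We will continue to monitor these outcomes throughout the implementation".

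**The concern.** A check of observed rates against assumed rates needs the assumed rates. None is given, so whoever writes the annual report has nothing to compare with.

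The randomised control arm could supply the comparison, but nothing in section B or D says that events are tabulated by arm or set against a denominator. This matters because of the population. The plan itself recognises events that arise from the families' circumstances, and it has procedures for depression, partner violence and suicidal behaviour. Such events will occur in both arms. Judged one at a time, each may reasonably be called unrelated to the protocol even if one arm has clearly more of them. Only a split by arm shows that pattern.

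At stake is whether an excess of common, expected-type events among COPE mothers or infants would be noticed while the trial is running.

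**Working it through.** The plan states no adverse-event rate, harm threshold or safety power, so it has no figure to reproduce. The calculations below are illustrations.

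**Inputs from the documents**
- 300 mother/infant pairs enrolled (Human Subjects section A).
- Two-sided alpha of .05, stated for efficacy (C.6, Power Analysis).
- Design effects of 1.4 and 1.8 (same place). They follow from 1 + (n − 1) × ICC with n = 9: 1 + 8 × .05 = 1.4 and 1 + 8 × .1 = 1.8.

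**Assumptions**
- A 1:1 split, hence 150 per arm.
- Control-arm proportions with at least one event of 2%, 5%, 10% or 20%.
- A doubling under COPE.

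**Step 1: what an unsplit total can show.** At a pooled rate of 15%, 300 × .15 = 45 participants have an event. An equal split is about 22.5 per arm (15% each). A doubled risk is 15 against 30 (10% against 20%). The total is the same, so a list or summary that is not split cannot separate the two.

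**Step 2: what the stated check could do if a benchmark existed.** A doubling confined to COPE raises the pooled rate to (p + 2p)/2 = 1.5p. Suppose the control rate p were known exactly, and a pooled count were flagged when its binomial tail probability under p is at most .025 (300 participants, no clustering). The flags would fall at 12, 24, 42 and 75 participants with an event. The chances of a flag are in the table below.

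These chances are not poor. However, the same pooled rate of 1.5p, and so the same chance of a flag, arises with no COPE effect at all if the true background in both arms is 1.5 times the assumed value. The check is only as good as the benchmark, and the plan does not give one.

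**Step 3: what a split by arm could do.** With m = 150 / design effect and p̄ the mean of the two rates:

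power = Φ{ [ |p₁ − p₀| − 1.96 √(2p̄(1 − p̄)/m) ] / √([p₀(1 − p₀) + p₁(1 − p₁)]/m) }

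For 5% against 10%:
- Design effect 1, m = 150: (.05 − 1.96 × .03041)/.03028 = −.317, power .375.
- Design effect 1.8, m = 83.3: (.05 − 1.96 × .04080)/.04062 = −.738, power .230.

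| Control vs COPE | Pooled rate | Pooled check, benchmark known | By arm, DE 1 | DE 1.4 | DE 1.8 |
|---|---|---|---|---|---|
| 2% vs 4% | 3% | 19% | 17% | 14% | 11% |
| 5% vs 10% | 7.5% | 40% | 38% | 28% | 23% |
| 10% vs 20% | 15% | 71% | 68% | 54% | 44% |
| 20% vs 40% | 30% | 98% | 97% | 90% | 81% |

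The split by arm therefore brings no gain in power over a perfect benchmark. Its advantage is that it needs no benchmark and that a difference points to the randomised intervention. At low event rates it has little power to confirm an imbalance, so the table should be read as description and not as a test.

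**The case against.** The strongest reply is that item 1 is one line of an annual report and far from the only safeguard. Events are graded for attribution and severity, and severe or unanticipated ones go promptly to the IRBs and NIH. The investigators review safety monthly, an internal committee weighs risk against benefit quarterly, and there is a safety officer. Adverse events will also be included in the posted summary results (section E). Infant growth, a plausible place for harm from a feeding intervention, is compared by arm as an outcome under Aim 1. C.2 promises continued monitoring of benchmark areas that include emergency department visits. All of this stands. It means that individual serious events would be seen and that some harm-related outcomes have partial cover. It does not fill the gap, because the individual reporting works case by case and the benchmark monitoring names no comparison by arm, no schedule and no reviewer.

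A second reply is that the DSMB's general duty to monitor safety leaves it free to ask for data by arm. That is correct: the plan does not exclude it. The supportable statement is that such data are not provided for. The listed membership includes no statistician, which is a reason to settle the table in advance.

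A reader might also infer that arm-level data could not be discussed on the calls without unblinding the study team. The documents do not support this. Only assessment workers are stated to be blind (C.1), and C.2 has the investigators' side training COPE visitors and reviewing their sessions. The team's presence on the calls does not itself hide harm. It bears on the board's independence and on the confidentiality of accumulating comparative data.

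**Conclusion.** The point holds in a limited form. The stated check has no yardstick, and neither the annual report nor the DSMB remit provides for adverse events by arm. What could be missed is an excess of expected-type events in the COPE arm.

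Two stronger conclusions may tempt a reader, and the documents support neither. One is that harm in general would go unseen; individual reporting and the safety officer speak against that. The other is that the minimal-risk statement would rest on data unable to contradict it. In sections B and D that statement is a judgement made in advance from the nature of the activities, not a finding from event data.

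The size cannot be fixed, because no event rates are given. With 150 per arm (1:1 assumed) and a doubling of risk, power for a comparison by arm runs from 11% to 17% at a 2% control rate, 23% to 38% at 5%, 44% to 68% at 10% and 81% to 97% at 20%, for design effects from 1.8 down to 1. The rates, the doubling and the allocation ratio are all assumptions. The gap in the plan does not depend on them.

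**What to change.** In section D (Safety reviews), replace item 1 with a descriptive table of adverse and serious adverse events by randomised arm, separately for mothers and infants. Give the number and share of enrolled participants with at least one event (about 150 per arm if 1:1). Use those enrolled and not the expected effective sample of 200, since events can occur before dropout. Add a cluster-adjusted difference with 95% confidence interval at the final analysis only. During rolling enrolment, with few events spread over 30 visitors, such an interval every six months would be unstable.

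In Monitoring plan item 5, provide this table to the DSMB at its existing twice-yearly meetings, in a closed part of the call without the research team. Justify this by the board's independence and the confidentiality of comparative data. The team can remain for recruitment and progress.

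The cost is one extra table per meeting, drawn from the adverse-event log already kept, and a few lines of wording. The limitation should be stated with it: at low event rates the table shows an imbalance but can seldom confirm one.
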